9.3.3 Outcome Measures

The primary outcome measure will be diagnostic accuracy (point estimates and exact 95% CIs) determined across all images (at least 200 images), as indicators of the collective proficiency of the clinical readers at interpreting VIZAMYLTM PET images. Diagnostic accuracy will give an indication of the overall image interpretation error rate (1 minus diagnostic accuracy). Additional outcome measures will be sensitivity, specificity, PPV, and NPV.

9.3.4 Risk Factors

Demographic variables about the clinical readers will be analysed to try to determine reader-associated variables associated with image interpretation errors.

9.3.5 Co-Morbidities

Except for structural abnormalities of the brain (which can be detected on MRI and/or CT and possibly adjusted for during PET image interpretation), there are no known co-morbidities that would affect PET image interpretation.

The AE profile in patients with renal impairment and/or hepatic impairment is currently unknown. In accordance with the current risk management plan for VIZAMYLTM, a history of renal impairment and/or hepatic impairment will be captured in the eCRF. For documentation of AEs in these patients see Section 11.1.4.

9.3.6 Co-Medications

There are no known drug interactions that would affect image interpretation and so data on comedications will not be collected.

9.3.7 Potential Confounders and Effect Modifiers

Potential factors that may affect image interpretation are brain atrophy, enlarged ventricles, and intracranial masses (which may distort brain anatomy). These can be detected on MRI and/or CT scans (which should be available for most if not all subjects as they are a standard component of patient workup for cognitive impairment) and taken into account during PET image interpretation.

9.4 Data Sources

9.4.1 Strategies and Data Sources

Data from subjects and clinical readers can be obtained prospectively, or existing data can be used. Expert image reads will be obtained prospectively from expert readers who consent to participate. Data sources will be the images and patient medical records. Image interpretations and other data will be recorded directly onto eCRFs; images will be provided electronically. All measurements are considered standard for assessment of a diagnostic test.

Consenting eligible clinical readers (1 to 5 per country) will be selected and demographic information about them will be collected. They will each read VIZAMYLTM PET images obtained in clinical practice to generate the primary data that will be used to determine diagnostic accuracy.

Participating subjects will have been administered VIZAMYLTM intravenously and will have subsequently undergone PET brain imaging. Demographic information about the subject will be obtained from the imaging site where the subject is/was scanned. All VIZAMYLTM PET images (at least 200 images) and any associated anatomic images (brain CT and/or MRI) in this study will be acquired as part of clinical practice in Europe.

9.4.2 Expert Committees

Five consenting expert readers will each be asked to separately and independently read the images obtained in clinical practice from the subjects, and their majority image interpretations will be used as the SOT for determining diagnostic accuracy, sensitivity, specificity, PPV, and NPV. The interpretation of the images by the expert readers may be split up into multiple small reads for convenience as well as to accrue data steadily throughout the study.

9.5 Study Size

Number of Subjects

This study has no formal hypothesis and no statistical tests will be performed. The endpoints of accuracy, sensitivity, and specificity will be summarised descriptively with point estimates and

95% CIs. Although no formal hypothesis will be tested, the sample size is determined to achieve the desired precision in estimating the primary endpoint of the percentage of subjects whose images are correctly classified as positive or negative (accuracy). Assuming that VIZAMYLTM images from 90% of subjects are read correctly by readers who have taken the VIZAMYLTM training programme, 200 subjects will achieve a 95% CI width of less than 10%.

The endpoints of sensitivity and specificity will also be summarised descriptively. This study aims to characterise reader performance in clinical practice so the number of positive and negative images will not be controlled. However, it is expected that most patients who are referred for a VIZAMYLTM scan will have dementia, and most cases of dementia are AD. Since brain amyloid is present in AD, it is expected that the majority of patients in this study will have brain amyloid. It is assumed that the majority blinded interpretation of the expert readers will be SOT-positive for approximately 65% of scans, giving a total of approximately 130 scans for sensitivity, with the remaining 70 scans being SOT-negative and therefore usable for calculating specificity. Assuming a sensitivity of 90% and a specificity of 90%, these sample sizes should give reasonably precise 95% CIs for estimating sensitivity and specificity in this scenario (95% CI width of approximately 15% or less).

Accuracy, sensitivity, and specificity will also be calculated by country where all study images from sites within a given country will be pooled for analysis. No country may contribute more than 25% of the total number of images. Because the number of subjects per country is smaller than the overall number of subjects, the level of precision and the width of the CI will be impacted. Again, since the aim of the study is to characterise reader performance in clinical practice, the exact number of images obtained per country and per site is unknown. Table 6 provides examples of 95% CI widths for accuracy assuming a few different sample sizes per country to illustrate the change in precision.

Table 6 95% Confidence Interval Width for Different Sample Sizes Assuming 90% Diagnostic Accuracy

| | | Lower Confidence | Upper Confidence |
|-------------|---------------------|------------------|------------------|
| Sample Size | Actual 95% CI Width | Limit | Limit |
| 30 | 24.4% | 73.5% | 97.9% |
| 40 | 20.9% | 76.3% | 97.2% |
| 50 | 18.5% | 78.2% | 96.7% |
| 60 | 16.7% | 79.5% | 96.2% |

When calculating sensitivity and specificity per country, precision will again be impacted because the sample size per country will be further divided into SOT-positive and SOT-negative scans. For example, if a country enrols 40 subjects and 65% of the scans are SOT-positive (n = 26) then the width of the 95% CI for sensitivity would be 26.4% (lower confidence limit = 71.8%) and the width for specificity would be 37% (lower confidence limit = 62.4%).

Accuracy by reader will also be presented in a tabular form, though it may be expected that some institutions will have very few scans per reader.

GE Confidential Page 27 of 43

Number of Clinical Readers

The number of clinical readers (1 to 5 per country) was chosen to allow each European country where VIZAMYLTM is commercially available to be represented.

Number of Expert Readers

The number of expert readers (5) was chosen based on precedent set in prior clinical studies of VIZAMYLTM.

9.6 Data Management

9.6.1 Data Collection

Non-imaging data will be collected directly from sites, clinical readers, and expert readers using eCRFs. Images will be transferred from imaging sites to the Sponsor using electronic transfer protocols.

9.6.2 Data Monitoring

Data will be monitored for completeness and logic using electronic edit checks, manual data listing review, and source data verification.

9.6.3 Data Retrieval from Sites

This is described above in Section 9.6.1.

9.6.4 Data Preparation

When necessary, the Sponsor or a designee will remove identifying information from the ≥200 VIZAMYLTM PET images, which thereafter will be designated only by subject number.

The images received by the GE Healthcare core lab will have been transferred by a system which de-identifies the images. This will be confirmed in a quality control step when images are received.

9.6.5 Data Management and Statistical Hardware

An electronic data capture (EDC) system will be used to collect data. A single data management contract research organization (CRO) will oversee the data collection at all sites. The data management CRO will be responsible for developing the database, training site personnel to enter data, data cleaning, and query resolution. The handling of data, including data quality control, will comply with all applicable regulatory guidelines. Appropriate access controls will be built into the database to ensure image blinding is maintained. The data management process will be outlined in more detail in the Data Management Plan.

9.7 Data Analysis

The data will be analysed by the sponsor-designated CRO. Any data analysis carried out independently by the investigator should be submitted to the Sponsor before publication or presentation.

Data from participating centres in this protocol will be combined so that an adequate number of subject images will be available for analysis. The data will be summarised with respect to demographic characteristics and efficacy observations and measurements.

General Statistical Considerations

Tabulations of summary statistics, graphical presentations, and statistical analyses will be performed using SAS® software, Version 9.3 or higher. Descriptive statistics for continuous data in summary tables will include the number of subjects in the analysis (n), mean, standard deviation, median, and range (minimum, maximum). Descriptive statistics for categorical data in summary tables will include counts and percentages. All data entered into the database will be provided in separate data listings showing individual subject values. The planning and reporting of statistical analysis will be carried out as described in the Sponsor and CRO's standard operating procedures (SOPs) governing clinical studies. Details of the analysis will be provided in the Statistical Analysis Plan.

Missing values will not be substituted by estimated values, but treated as missing in the statistical evaluation. All data from all subjects enrolled and imaged in the study will be included in all listings, plots, summary tables, and statistical analyses when appropriate.

Subjects who do not meet the definition of the evaluable population will be excluded from the analyses. This will be determined prior to database freeze and image unblinding.

Any deviations from the statistical analysis outlined in this protocol will be described, and reasons for the deviations listed, in the final Clinical Study Report.

Populations for Analysis

The safety population will consist of all subjects who were enrolled in the study and received a dose of VIZAMYLTM.

The efficacy subject population will consist of all subjects who have an interpretable image that has an available expert majority image interpretation.

The efficacy clinical reader population will consist of each clinical reader who has interpreted the images included from his/her institution and has had their image interpretations classified as TP, TN, FP, or FN through comparison with the SOT (the expert reader majority interpretation).

Page 29 of 43

Subject Demographics/Other Baseline Characteristics

A table will be provided with the following information:

- Number of subjects enrolled.
- Number of subjects in the safety population.
- Number of subjects with VIZAMYLTM images included in the efficacy analysis.

GE-067-027 C

Version 7.0 Approved

Demographic information (Table 5 above) will be summarised using descriptive statistics.

Study Treatments

All subjects will have received VIZAMYLTM as part of routine clinical practice. The dose and volume administered will be summarised across all subjects.

Clinical Reader Demographics/Other Baseline Characteristics

A table will be provided with the following information:

- Number of clinical readers participating.
- Number of clinical readers' image interpretations included in the efficacy analysis.

Demographic information (Table 5 above) will be summarised using descriptive statistics. Demographic information will be reported for readers who are randomly chosen to participate as well as the complete pool of potential readers who agreed to participate in addition to readers who decided not to participate where data are available.

Primary Analysis

The primary analysis will be the determination of diagnostic accuracy, sensitivity, specificity, PPV, and NPV across readers based on all evaluable images (at least 200 images) (point estimates and exact 95% CIs).

Secondary Analyses

The numbers and percentages of images for which 5 expert readers agree, 4 expert readers agree, and 3 expert readers agree will be summarised. In addition, results will be analysed by the following variables:

- Country
- Time from training to image interpretation (<6 months, >6 months)
- Specialty of the reader
- Training method(s) used by the clinical reader (in-person, electronic, or both)

- Number of scans read by the clinical reader in practice prior to the study (<50, >50)
- Reader classification certainty (1 to 5)

The by-variable summaries will include estimates of diagnostic accuracy, sensitivity, specificity, PPV, and NPV along with 95% CIs for data pooled within each category. They will also show the number of clinical readers in each category and the number and percentage of clinical readers in each category with diagnostic accuracy <70%, >70% to $\le80\%$, >80% to $\le90\%$, and >90%.

The certainty of image classification will be summarised.

Safety Analyses

The number and percentage of subjects with 1 or more treatment-emergent AEs will be summarised. Additionally, treatment-emergent AEs will be coded and summarised by system organ class and preferred term. Treatment-emergent AE summaries will be provided by relationship to study drug and severity. Treatment-emergent serious AEs (SAEs) will also be summarised.

Interim Analysis

No formal interim analyses of the data are planned for this study. Interim progress reports of enrolment and safety will be provided annually.

Analyses of Study Limitations

Please see Section 9.9 below.

Evaluation of Impact of Study Results on Marketing Authorisation

The Sponsor will evaluate whether the study results have an impact on the marketing authorisation and will, if necessary, submit to the EMA an application to vary the marketing authorisation.

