8 RESEARCH QUESTIONS AND OBJECTIVES

The research question to be answered by this study is: *How effective is the VIZAMYL*TM reader training programme in clinical practice in Europe? To answer this question, the study has the following primary and secondary objectives.

Primary:

The primary study objective is to assess the effectiveness of the VIZAMYLTM reader training programmes (in-person or electronic) in Europe by estimating the diagnostic accuracy, sensitivity, specificity, PPV, and NPV, of the visual interpretation of VIZAMYLTM images obtained in the course of clinical practice. Diagnostic accuracy is the overall true-interpretation rate for all subjects. One minus the diagnostic accuracy gives the overall image interpretation error rate.

Secondary:

The secondary study objective is:

Evaluate the impact of demographic and other factors (such as method of training, gap between training and reading, and country) on diagnostic accuracy to try to identify factors that may be associated with image interpretation errors.

Sensitivity is the true-positive (TP) image interpretation rate in subjects with brain amyloid. Specificity is the true-negative (TN) image interpretation rate in subjects without brain amyloid. Positive predictive value (PPV) is the TP image interpretation rate for subjects with positive VIZAMYLTM scans. Negative predictive value (NPV) is the TN image interpretation rate for subjects with negative VIZAMYLTM scans.

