2.2 Secondary objectives

Evaluate the impact of demographic and other factors (such as method of training, gap between training and reading, and country) on diagnostic accuracy to try to identify factors that may be associated with image interpretation errors.

Sensitivity is the true-positive (TP) image interpretation rate in subjects with brain amyloid. Specificity is the true-negative (TN) image interpretation rate in subjects without brain amyloid. Positive predictive value (PPV) is the TP image interpretation rate for subjects with positive VIZAMYL™ scans. Negative predictive value (NPV) is the TN image interpretation rate for subjects with negative VIZAMYL™ scans.

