8.6.3 Secondary analysis

Images for which 5 expert readers agree, 4 expert readers agree, and 3 expert readers agree will be summarised using counts and percentages.

In addition, estimates of diagnostic accuracy, sensitivity, specificity, PPV, and NPV, along with exact 95% CIs, will be provided separately for prospective images, retrospective images, and pooled results, separately, using the following variables:

- Country
- Time from training to image interpretation (<6 months, \geq 6 months)
- Specialty of the reader
 - Nuclear Medicine
 - Radiology
 - Medical Physics
 - Other
- Training method (s) used by the clinical reader (in-person, electronic, or both)
- Number of scans read by the clinical reader in practice prior to the study (<50, \geq 50)
- Clinical reader and SOT classification certainty (1 to 5)

The number of clinical readers in the above subgroups will be provided. The number and percentage of diagnostic accuracy categories <70%, >70% to \leq 80%, >80% to \leq 90%, and >90% will also be provided by using the above subgroups for prospective images, retrospective images, and pooled results, separately.

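### The by-variable analysis describes accuracy within each category but does not quantify the impact of any factor, and its exact intervals ignore clustering of images by reader

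*Protocol*

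**What the plan says.** Protocol section 8 sets the secondary objective: "Evaluate the impact of demographic and other factors (such as method of training, gap between training and reading, and country) on diagnostic accuracy", with the stated purpose "to try to identify factors that may be associated with image interpretation errors". SAP 2.2 repeats it. Protocol 9.3.4 adds: "Demographic variables about the clinical readers will be analysed to try to determine reader-associated variables associated with image interpretation errors". It names no method.

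Protocol 9.7 (Secondary Analyses) lists six variables: country, time from training to reading, specialty, training method, number of scans read before the study, and reader certainty. For these it states: "The by-variable summaries will include estimates of diagnostic accuracy, sensitivity, specificity, PPV, and NPV along with 95% CIs". The data are pooled inside each category, and the tables also give the number of readers in each category and how they fall into accuracy bands.

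SAP 8.6.3 follows the same pattern: "estimates of diagnostic accuracy, sensitivity, specificity, PPV, and NPV, along with exact 95% CIs, will be provided separately" for prospective, retrospective and pooled images. SAP 8.6.1 describes all efficacy analyses as descriptive, and SAP section 9 reports no change from the protocol. On inference, Protocol 9.5 says "This study has no formal hypothesis and no statistical tests will be performed", and SAP section 5 says the same. Accuracy by reader is also to be tabulated (Protocol 9.5, SAP section 5).

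**The concern.** The impact of a factor, or its association with errors, is a statement about how accuracy differs between categories. The plan estimates accuracy inside each category and stops there. Anyone using the report would have to compare intervals by eye, which can mislead in two ways:

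- Two separate 95% intervals can overlap although the interval for the difference excludes zero.
- Country, specialty, training method and prior scan count belong to the reader rather than the image. A category's images may therefore come from only a few readers. If accuracy varies between readers, exact binomial intervals are too narrow, and a gap between two categories may reflect those few readers.

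The study was requested by the regulator to evaluate reader training, so a report that finds no factor could be taken as evidence that training method or training gap does not matter. Without an interval for the difference, nothing shows how large an effect remains compatible with the data. The primary estimate of overall accuracy is not affected.

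**Working it through.** **1. The plan's own precision figures.** Clopper-Pearson 95% intervals at 90% accuracy reproduce Protocol Table 6 (SAP Table 5-1): widths 24.4%, 20.9%, 18.5% and 16.7% for n = 30, 40, 50 and 60. For n = 200 the interval is 85.0-93.8%, width 8.8%, consistent with the stated width below 10%. All of these describe a single proportion. Neither document gives precision for a contrast.

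**2. Number of readers and errors.**
- The reader cap is 7.5%, or 15 of 200 images (Protocol 9.2.5). 200/15 = 13.3, so at least 14 readers are needed.
- Expected errors at 90% accuracy: 200 × 0.10 = 20.
- With 1 to 5 readers per country, a country category could consist of one reader.

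**3. Separate intervals against an interval for the difference.** The counts are assumed, because the documents give no category sizes: 94/100 and 85/100 correct.
- Exact intervals: 87.4-97.8% and 76.5-91.4%. They overlap between 87.4% and 91.4%.
- Difference = 9.0 points. SE = sqrt(0.94 × 0.06/100 + 0.85 × 0.15/100) = 0.0429.
- 95% CI under independence: 9.0 ± 1.96 × 4.29 = 0.6 to 17.4 points.

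**4. Allowing for reader.** Assume 16 readers with 200/16 = 12.5 images each, and a within-reader correlation r, for which the documents give no value. Design effect = 1 + 11.5r; the SE is multiplied by its square root.

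| r (assumed) | Design effect | 95% CI for the difference (points) |
|---|---|---|
| 0 | 1.000 | 0.6 to 17.4 |
| 0.02 | 1.230 | -0.3 to 18.3 |
| 0.05 | 1.575 | -1.5 to 19.5 |
| 0.10 | 2.150 | -3.3 to 21.3 |

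The lower limit reaches zero when the design effect is (9.0/(1.96 × 4.288))² = 1.147, that is r = 0.147/11.5 ≈ 0.013.

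**5. Precision to expect if differences are added.** Half-width = 1.96 × sqrt(0.09/n1 + 0.09/n2), with both categories at 90%. The splits are assumed. The last column multiplies by sqrt(1 + 14r), taking 15 images per reader and r = 0.05 to 0.10.

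| Split | Half-width, independence | With clustering |
|---|---|---|
| 100 vs 100 | ±8.3 | ±10.8 to ±12.9 |
| 150 vs 50 | ±9.6 | ±12.5 to ±14.9 |
| 170 vs 30 | ±11.6 | ±15.2 to ±18.0 |
| 50 vs 50 (two countries at the cap) | ±11.8 | ±15.3 to ±18.2 |
| 30 vs 30 | ±15.2 | ±19.8 to ±23.5 |

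**The case against.** A reader might infer that the secondary objective cannot be answered at all, or that the within-category estimates are its only analysis. The documents support neither inference. The objective is worded tentatively, the study is declared descriptive, and category estimates with intervals are a descriptive answer. The plan also gives the number of readers per category, their spread over accuracy bands, and accuracy by reader. These help show whether a category result rests on a few readers. Protocol 9.9 discloses that reader subgroups may be unbalanced. A crude difference can be obtained by subtraction from the tables.

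The example should not be over-read either. Its counts, equal split, number of readers and correlation are assumptions, and it sets conservative exact intervals beside a Wald interval. A correlation of about 0.013 is enough to bring zero into the interval, so the recommended analysis might show no clear difference. The example does not show that the tables would hide a real effect. It shows that they leave the size and uncertainty of a difference unstated.

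A multivariable model would be hard to support with about 20 errors, and a logistic model does not directly give a difference in accuracy. Both points stand and limit the fix.

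The no-tests statement does not justify the omission. A difference with a confidence interval is estimation, and the plan already reports confidence intervals throughout. Nor do the reader bands and by-reader tables supply an interval for a contrast, or widen the exact intervals to allow for reader.

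**Conclusion.** The point holds as a mismatch between objective and analysis. The plan describes accuracy by category but does not quantify the impact of any factor. Its exact intervals treat images from the same reader as independent, although four of the six listed factors are reader properties and as few as 14 readers could supply 200 images.

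The absence of a contrast follows directly from the two documents and needs no assumption. The effect of clustering does depend on assumption: in the example, correlations from 0 to 0.10 move the interval from 0.6 to 17.4 points to -3.3 to 21.3 points. The issue is confined to the secondary objective, but it merits correction because that objective is stated in both documents and the remedy uses data already to be collected.

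**What to change.** In SAP 8.6.3, keep the planned tables and add the following:

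- For one factor at a time, on the pooled prospective and retrospective images, estimate the difference in accuracy in percentage points from a stated reference category, with a 95% CI that allows for clustering by reader. Suitable methods are an identity-link GEE with a small-sample correction or a reader-level bootstrap.
- Label these estimates exploratory and give no p-values, which keeps the no-tests statement intact.
- State in advance how sparse levels will be collapsed. Where a level has too few readers or errors, report counts only. This is likely for some countries and certainty levels.
- Treat adjustment for data source (prospective or existing) as optional, for use where readers contribute to both.

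Record the addition in SAP section 9. The cost is a few paragraphs of SAP text and some programming, with no new data. The downside is wide intervals, about ±8 to ±15 points before clustering depending on the split, and some factors that cannot be estimated. If the sponsor prefers not to add this, the secondary objective should be reworded as a description of accuracy by category.
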